## **Chapter 1. STUDY OVERVIEW**

Globally, over three million children sustain a traumatic brain injury (TBI) each year, with an estimated 3-7% being classified as having a severe TBI (Glasgow Coma Scale (GCS) score  $\leq 8$ ). Long-term TBI-related disability and high health care costs are a significant burden to individuals and society, although data are limited outside of the United States and Europe. The Brain Trauma Foundation (BTF) Guidelines for Management of Pediatric Severe TBI represent the most comprehensive synthesis of evidence-based care for children with severe TBI, but they are not systematically implemented and are also almost exclusively based on evidence from research in the United States and Europe.

Pediatric Guideline Adherence and Outcomes (PEGASUS) Argentina is a National Institutes of Health (NIH)-funded, multi-site randomized controlled trial (RCT) currently testing implementation of best practice care for children with severe TBI in South America. In prior work, we found that adherence to the TBI guidelines was associated with 6% better outcomes in 5 leading U.S. academic centers. The single center PEGASUS program pilot at Harborview Medical Center (Level-1 pediatric trauma center in Seattle, Washington) demonstrated improved adherence to key performance indicators of the BTF guidelines and patient outcomes, while not increasing in-hospital costs. However, TBI guideline adherence remains low, and the guidelines have limitations related to recommendation applicability across health care systems and across countries. While feasible, acceptable, and efficacious in the pilot study, the next step is to test PEGASUS intervention effectiveness more broadly. Focus on our partnership with experienced TBI researchers in Argentina at the Centro de Informática e Investigación Clínica (CIIC), and implementation at South American hospital sites will expand evidence of which guidelines are most important contributors to three-month patient outcomes and examine generalizability of the PEGASUS program.

The study hypothesis is that the PEGASUS program improves TBI guideline adherence during the first 3 days of intensive care in all children severe pediatric TBI and stratified by extracranial injury status. Sixteen hospitals throughout Argentina (14), Chile (1), and Paraguay (1) are participating in this study (Chapter 3.2).

### **1.1 Specific Aims**

- 1) Determine the relationship between PEGASUS program implementation and TBI guideline adherence (Aim 1a) and assess system, provider, patients, implementation, and guideline factors associated with TBI guideline adherence (Aim 1b).
- 2) Create a value stream map (VSM) that readily identify value added process of care associated with TBI guideline adherence.
- 3) Use computer simulation to develop and disseminate a real-world best practices blueprint for TBI guideline adherence.

This is a necessary advance and a step towards implementing guideline-based TBI care for children who suffer from TBI.

\*\*A cost analysis component is also included, although it is not a separate aim.

## **1.2 Funding**

Research is supported by the National Institute of Neurological Disorders and Stroke of the National Institutes of Health under award number R01NS106560 (PIs: [name] and [name]). Primary award is to the University of Washington (UW), subcontracts awarded to support CIIC, CNH, and WSU. Study hospitals receive funding through CIIC based on patient enrollment as well as subsidized travel.

The sponsor and funder had no role in the design of this study and will not be involved in the implementation, analyses, interpretation of data, or writing of manuscripts for publication.

## **1.3 IRB Protocol**

The study protocol (UW IRB# STUDY00005629) was initially approved by the UW Institutional Review Board (IRB) on 09/28/2018 as minimal risk. Study design revision was approved on August 7, 2020 and modification assessed as minimal risk. Approval was obtained at the IRBs for each of the local study hospitals for local recruitment, consent, and activities.

# **Chapter 2. STUDY ORGANIZATION AND RESPONSIBILITIES**

## **2.1 Coordinating Center**

The University of Washington is the Coordinating Center. Roles and responsibilities include:

- Development of the randomization scheme and procedures
- Development of intervention plan
- Development of the data flow and data management procedures, including data entry, error identification, and correction
- Development of data collection forms
- Development of value stream mapping app
- Communications with secondary centers, scheduling of meetings, and responding to ad hoc communications
- Quality control procedures
- Statistical analysis
- Subject matter expertise
- Reports (e.g. enrollment, participant status, site performance, quality control, DSMB)
- Distribution of updates, documents, and reports to secondary sites, study sites, DSMB, IRB, FITBIR, NIH, as necessary

## **2.2 Secondary Centers**

Centro de Informática e Investigación Clínica (CIIC) is responsible for:

- Communications with study sites, study IRBs, and coordinating center
- Co-development of intervention, procedures, and forms

- Training of study sites
- Site visits to ensure adherence to protocol and procedures
- Database development and management
- Data entry and cleaning
- Subject matter expertise
- Translation

Children's National Hospital (CNH) provided:

- Subject matter expertise
- Co-development of intervention, procedures, and forms

Washington State University (WSU) provided:

- Cost analysis and utilization

### **2.3 Study Sites**

The study sites (site PI and site coordinators) are responsible for:

- Participation in the protocol finalization and preparation of study materials
- Compliance with protocol and IRB regulations
- Recruitment, screening, and enrollment of participants
- Protection of participants' rights
- Training of pediatric intensive care unit (ICU) staff and intervention implementation
- Data collection and participant follow-up through study completion
- Transfer of data to secondary center (CIIC)
- Communication of questions, concerns, and observations to secondary and coordinating centers.

## CHAPTER 3. STUDY DESIGN

[figure not shown]
### 3.1 Study Design

This study is an open-label, multicenter, phase 3, superiority, pragmatic, parallel cluster randomized controlled trial (RCT) including 16 South American hospitals to provide usual care (n=8 sites) or the PEGASUS intervention (n=8 sites). This final design resulted after two iterations: the first iteration was a parallel cluster RCT with twelve sites (6 intervention, 6 control). In response to site requests for receiving the PEGASUS Pathway intervention, a stepped wedge design was developed and approved by the sponsor. However, the final study design was again updated in August 2020 after approvals from site PIs and sponsor from a stepped-wedge design due back to a parallel cluster RCT with sixteen sites (8 intervention, 8 control) due to COVID-19 pandemic challenges.

### 3.2 Governance Model

[figure not shown]
The University of Washington and Children's National Hospital supports CIIC's coordination of the sixteen hospital study sites for translation, project implementation, data management, data analysis, and data safety monitoring components.

### 3.3 Site Randomization Plan

Sixteen study sites were recruited by CIIC based on willingness to participate and annual severe TBI admissions. Sites were added after the original proposal to increase the potential patient recruitment population. All sites receive compensation for data submission. Prior to randomization on July 13, 2020, three sites who had no or one enrolled patient during ten months of baseline usual care data collection were removed from the pool. The remaining sixteen sites participating were ranked by median monthly baseline enrollment, number of zero recruiting months, and total number of recruited patients and divided into four groups (Group A=highest enrollment group, Group D=lowest enrollment group). The study statistician performed computer block randomization within each group to assign to control and intervention arms at a 1:1 ratio. Participant assignment was dependent on the intervention or control arm assignment of the study hospital to which they were admitted.

Due to the nature of the intervention study team, site staff, and patients' families are aware of the site's arm assignment.

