### **3.7 Sample Size and Power**

A sample size of 432 participants is targeted for the planned parallel cluster study, which would have 80% power to detect a 18.7% higher ICU TBI guideline adherence rate with program implementation at the site level, with a two-sided alpha of 5%, and an intraclass coefficient of 0.05. Calculations included 58.6% guideline adherence rate estimate based on prior pilot work in Argentina and assumed no change in adherence rate at control sites. The study will not be sufficiently powered for secondary outcomes of patient mortality, discharge outcomes, or three-month follow-up outcomes.

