**Questions of interest:**

- 1) Does PEGASUS implementation improve guideline adherence?
- 2) Are there any imbalances between the study arms that need to be addressed?

**Study Design:** 2-arm parallel cluster RCT

**Study population:** Pediatric (<18) ICU patients with severe TBI at 16 sites

**Exposure variable(s):** Study Arm (binary)

**Outcome variable(s):** (1) TBI guideline adherence

*"The main outcome is TBI guideline adherence during first 3 days ICU stay, calculated via our previously developed TBI guideline adherence scorecard. Using patient charts, we measure presence or absence of adherence to the indicators and capture time since injury for any observed indicators, including the main protective KPIs (ventilation, nutrition, CPP). Patient guideline adherence is defined as the sum of indicators to which care was adhered divided by the number of relevant adherence indicators for a given patient. Mean adherence scores are calculated for each site individually and across all sites."*

Describe:

- (2) Extracranial injuries
- (3) Discharge GOS
- (4) Discharge survival
- (5) 3-month GOSE-Peds
- (6) 3-month mortality
- (7) KPIs?

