**Covariates/confounders:**

- patient (demographics, ISS, LOS, presence of extracranial injuries, and surgery (yes/no) for up to 7 days after severe TBI in case report forms. If a child is discharged or dies prior to day 7, data collection will stop. Recorded radiographic evidence of cerebral edema, subdural hematoma, and intracranial hemorrhage on first head CT)
- implementation (reach, dose, fidelity from medical records),
- organizational (annual trauma volumes, and physician & nurse staffing)

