**Methods:**

1. Descriptive statistics for all measures at the facility level, within treatment and control arms. Potential differences in patient (age, sex, race/ethnicity) and injury characteristics will be examined using bivariate analyses by center using  $\chi^2$  tests (categorical) and t-tests (continuous).
2. ITT analysis: multi-level mixed effects Poisson regression with robust variance estimation and clustering by site to estimate the relative risk of PEGASUS implementation on TBI guideline adherence and stratified by extracranial injury, as described in Zou, et al.  
Per protocol: As with ITT, but potentially including implementation dose/fidelity as covariate and interaction with intervention.
3. Secondary analyses (Following ITT for primary analysis): Poisson regression with robust variance estimation and clustering by site to estimate separately the relative likelihood of program implementation on these outcomes: 1) in-hospital mortality; and 2) GOSE-Peds at 3 months post TBI, analyzing GOS score as a dichotomous measure (minor-moderate impairment vs major impairment-vegetative state and death).  
Multivariable Cox regression model to examine the marginal effect of PEGASUS on mortality during the 3 months post discharge, averaged over all centers.
4. Sensitivity analyses: repeated analysis on ICP monitoring patients
5. Subgroups: COVID effect and geographic effect

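### Sites were randomised within four enrolment groups, but the primary ITT model has no term for those groups

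*Protocol*

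**What the plan says.** Protocol section 3.3 states that the sixteen sites were "ranked by median monthly baseline enrollment, number of zero recruiting months, and total number of recruited patients and divided into four groups", labelled A (highest) to D (lowest). The statistician then used "computer block randomization within each group to assign to control and intervention arms at a 1:1 ratio".

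SAP Methods item 2 gives the primary ITT analysis as "multi-level mixed effects Poisson regression with robust variance estimation and clustering by site to estimate the relative risk of PEGASUS implementation", also run by extracranial injury status. The SAP names study arm as the exposure. It mentions neither the enrolment groups nor any small-sample correction for 16 sites.

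The nearest listed covariate is under "organizational (annual trauma volumes, and physician & nurse staffing", but the SAP does not say which listed covariates enter the ITT model. The outcome is a patient-level score, the "sum of indicators to which care was adhered divided by the number of relevant adherence indicators for a given patient". Protocol section 3.7 uses a "two-sided alpha of 5%, and an intraclass coefficient of 0.05" and does not mention the groups.

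**The concern.** Randomising within groups balances the arms on whatever the groups carry. If adherence differs between groups, that variation is removed from the true sampling error of the arm comparison. A model without the groups still counts it as noise, so a correctly calibrated test becomes conservative and its interval too wide. If adherence does not differ by group, the omission does no harm.

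Two things in the SAP might seem to cover this, but neither does. Stratifying by extracranial injury concerns a patient characteristic. Annual trauma volume is related to the grouping but is not the grouping, and nothing commits it to the ITT model.

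The remedy depends on a second gap. With 16 sites, an uncorrected robust variance is too small, and each added site-level term makes it worse. The group term and the variance correction therefore have to be decided together.

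**Working it through.** **Inputs from the documents.** 16 sites, 8 per arm; 432 patients, so 432/16 = 27 per site; control adherence 58.6%; difference 18.7 points; ICC 0.05; two-sided 5%.

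**The plan's own figure.** Design effect = 1 + (27 − 1) × 0.05 = 2.3. With p1 = 0.586, p2 = 0.773 and unpooled variance 0.586 × 0.414 + 0.773 × 0.227 = 0.418, n per arm before clustering = 7.849 × 0.418/0.187² = 93.8. Total = 2 × 93.8 × 2.3 = 431.7, which reproduces 432 at 80% power. The calculation treats adherence as binary and makes no allowance for the groups.

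**Assumed, because the documents do not give them.** Four sites per group, split 2:2; a linear trend across groups; share *s* of between-site variance explained by group = 0, 30 or 60%; for the proportion score, patient SD 0.35 or 0.30.

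**Hand check of interval width.** In units of the patient variance, a site mean has residual variance a = (1 − s) × 0.05 + 0.95/27 with the group term. Without it, the expected residual variance is u = a + 16 × s × 0.05/14. The width ratio (without/with) is about (t14/t11) × √(u/a), where t14/t11 = 2.145/2.201 = 0.974.

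| s | u | a | ratio |
|---|---|---|---|
| 0 | 0.0852 | 0.0852 | 0.97 |
| 30% | 0.0873 | 0.0702 | 1.09 |
| 60% | 0.0895 | 0.0552 | 1.24 |

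**Simulation.** Log-link Poisson, site-robust variance with Kauermann-Carroll correction, t on 14 df without the term and 11 df with A–D, 12,000 replicates per cell, 27 patients at every site:

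| | s = 0 | s = 30% | s = 60% |
|---|---|---|---|
| Width ratio, without/with | 0.98 | 1.09 | 1.23–1.24 |
| Type I error without term | 4.7–5.1% | 2.7–3.1% | 1.4–1.5% |
| Power, binary: without v with | 72 v 70 | 73 v 78 | 74 v 88 |
| Power, score SD 0.35 | 92 v 91 | 94 v 96 | 95 v 98 |
| Power, score SD 0.30 | 97.5 v 96.9 | 98.3 v 98.9 | 98.8 v 99.7 |

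Type I error with the term was 4.5–5.3% throughout. The term pays for its 3 df in width once the groups explain about 6% of between-site variance (10% at ICC 0.02, 5% at ICC 0.10).

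**Unequal sites.** The groups rank enrolment, so sizes will differ. With an assumed 50/30/18/10 patients per site in A/B/C/D, the width ratio is 0.98/1.06–1.07/1.18–1.20. Corrected type I error is 5.7–6.2/4.1–4.6/2.2–2.6% without the term and 5.3–6.6% with it.

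**Robust variance as written (no correction, z reference).** Type I error without the term is 8.3–8.9/5.7–5.8/3.2–3.3% (unequal sites 10.7–11.4/8.0–8.7/5.0–5.7%). Adding A–D alone gives 12.3–13.7% (unequal 14.4–16.1%).

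**Marginal fit in place of the mixed model.** For the score at SD 0.35, site means have variance 0.1225 × (0.05 + 0.95/27) = 0.0104. A Poisson model expects about 0.68/27 = 0.025 from sampling alone, so the random intercept collapses to zero. In 250 mixed-model fits per cell at s = 30%, the estimated site SD was below 0.02 in 100% of trials at SD 0.35 and in 76–99.6% for the binary outcome. The largest change in log relative risk was 0.021.

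**The case against.** The strongest reply is that the gain is small and conditional. The SAP outcome is a score, not a binary, and for it the power gain is 1 to 3 points from a base above 90%. The informative scenarios are also large. Under the linear trend, the A-to-D gap in adherence is 3 × √(s × 0.05 × V/1.25). For the binary outcome (V = 0.209) that is 15 points at 30% and 21 points at 60%, the latter above the 18.7-point target. For the score at SD 0.35 (V = 0.1225) it is 12 and 16 points. Nothing in the documents ties enrolment rank to adherence.

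This limits the size of the point but does not remove it. Break-even at 6% is a gap of only about 5 points for that score (3 × √(0.06 × 0.05 × 0.1225/1.25) = 0.051).

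With unequal sites and a 30% share, the corrected test without the term is already near 5%, and with the term it runs slightly above. That stands; the width gain there is 6 to 7%.

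The high error rates under the variance as written come from the missing small-sample correction, not from the missing groups. That also stands, and it is why the two changes must be made together.

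Finally, the SAP is silent rather than opposed, since it asks whether arm imbalances need attention. But leaving the choice until data are seen in an open-label trial is weaker than naming the one factor that the randomisation itself fixed.

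**Conclusion.** The concern holds as a modest, inexpensive improvement. The plan randomises within A–D and does not analyse by A–D. Under a small-sample-valid analysis with equal sites, the omission makes intervals about 9% wider at a 30% share and 23 to 24% wider at 60%. Type I error falls to about 3% and 1.5%. With strongly unequal sites, the excess width is 6 to 7% and 18 to 20%. Power for the SAP score changes by only about 1 to 3 points. If the groups explain nothing, no harm is done.

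The omission does not by itself create a false-positive risk. With the robust variance as written, however, the test without the term is not reliably conservative either. These figures rest on assumed group shares, a linear trend, 2:2 allocation in four equal groups, assumed patient SDs and assumed site sizes. They also rest on a marginal Poisson fit standing in for the mixed model.

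**What to change.** Add to SAP Methods item 2:

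> The primary ITT model will include the randomisation group (A, B, C, D; categorical) as a fixed effect. Inference for study arm will use a Kauermann-Carroll corrected site-robust variance and a t reference on 16 − 5 = 11 degrees of freedom.

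The five parameters are the intercept, study arm and three group terms. The group term should not be added without the correction.

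**Cost.** The groups are already known, so no new data are needed. The price is 3 df: if the groups are uninformative, intervals are about 2% wider and 1 to 2 points of power are lost (under 1 point at SD 0.30 with equal sites). With very unequal sites, type I error is about 6% (5.3–6.6%), much as it is without the term when groups are uninformative (5.7–6.2%).

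The correction must be named, because the choice matters. Mancl-DeRouen in place of Kauermann-Carroll gave 2.0–2.9% type I error and 12 to 16 points less power in the binary, equal-size case. The corrected variance was checked on the marginal fit, so the SAP should also say how it will be obtained for the model actually fitted.

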### **3.4 Screening and Eligibility Criteria**

All pediatric patients who admitted to the ICU at a study hospital site with a TBI are screened and their families/guardians are approached to enroll. Patients who are not eligible at admission but deteriorate are included at the time deterioration is assessed. No other exclusions.

To be included the patient must be:

- Age < 18 years
- Mechanism or CT evidence of TBI
- Glasgow Coma Scale (GCS) Score  $\leq 8$  (if intubated, motor GCS  $\leq 5$ )
- Admitted to ICU at any point in the hospital stay

An enrollment log will be kept in the secure database. Reasons for non-enrollment (does not meet eligibility criteria, death before consent, consent refusal, withdrawal) will be documented.

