### **3.5 Informed Consent**

If eligible, the 24-hour-on-call study coordinator is notified to begin a culturally appropriate consent process. Written informed consent for study procedures is obtained from legal guardians of patients by each participating site in Spanish. Verbal assent of the patient is also sought by ICU discharge if the patient is capable. Enrolled participants at the control sites consent to data collection from their medical records. Enrolled participants at the intervention sites consent to data collection and receive the intervention delivered by the trained ICU staff delivering their care. A patient or family/guardians can withdraw consent at any time. Should a patient or their family withdraw their consent, any previously collected data is removed from analysis and, if they are a patient at an intervention site, the PEGASUS clinical pathway is no longer used at the bedside, and they receive needed, usual care. The CIIC served as the regional coordinating center and storage warehouse for documentation. This protocol was performed according to the updated Declaration of Helsinki and all patients provided informed consent per local protocols for trial participation.

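### In-hospital mortality is compared only among children who survive to consent, so the ratio is biased if the share dying before consent differs by arm, and the SAP has no step to check this

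*Protocol*

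**What the plan says.** Protocol 3.4 provides for an enrollment log and adds: "Reasons for non-enrollment (does not meet eligibility criteria, death before consent, consent refusal, withdrawal) will be documented". Death before consent is listed separately from failing the eligibility criteria, so these are otherwise eligible children.

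Protocol 3.5 requires written guardian consent. The process starts as follows: "If eligible, the 24-hour-on-call study coordinator is notified to begin a culturally appropriate consent process". No time limit, deferred consent or waiver is described. What is consented to differs by arm. In control: "Enrolled participants at the control sites consent to data collection from their medical records". In the PEGASUS arm: "Enrolled participants at the intervention sites consent to data collection and receive the intervention delivered by the trained ICU staff delivering their care". After withdrawal, "any previously collected data is removed from analysis".

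Protocol 3.3 dates the site randomization to July 13, 2020, before the October 2020 start of the intervention, and notes that "site staff, and patients' families are aware of the site's arm assignment".

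The SAP hypothesis includes better discharge survival in PEGASUS centers. Methods item 3 plans a site-clustered Poisson model with robust variance "to estimate separately the relative likelihood of program implementation on these outcomes: 1) in-hospital mortality". It labels these secondary analyses as following ITT but does not define the ITT population. The only sensitivity analysis, in item 4, is restricted to patients with ICP monitoring. The SAP does not mention the enrollment log.

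**The concern.** Consent comes after assignment here, and it decides who is analyzed. A child who dies in the interval between eligibility and consent leaves both the numerator and the denominator of in-hospital mortality. If one arm obtains consent sooner, more of its early deaths are counted. The arm with slower consent then appears to have better survival, although nothing about care differed.

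There is a structural reason why timing might differ. Under Chapter 4 the pathway is delivered only to consented children, and the main outcome covers the first 3 ICU days, so intervention staff need consent early in order to act. Control staff need it only to abstract records. This does not fix a direction, since consent to a larger commitment could also take longer. The differing consent content bears more directly on refusal, which is a separate route of selection and is not quantified here.

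At stake is the reading of in-hospital mortality and discharge survival. Outcomes that count death, such as the 3-month GOSE-Peds category, share the problem.

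**Working it through.** **The plan's own figure.** The documents give no mortality rate, pre-consent death rate or mortality power. The one power statement (Protocol 3.7) concerns adherence and is not affected. It reproduces as follows. With 432/16 = 27 children per site, the design effect is 1 + (27 − 1) × 0.05 = 2.3, and the effective size is 216/2.3 = 93.9 per arm. For 58.6% vs 77.3% at two-sided 5%, the unpooled z calculation gives 80.0%.

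**Inputs for the check (all assumptions).** M is in-hospital mortality among eligible children, equal in both arms, at 30% or 20%. e is the share of eligible children who die before consent. Refusals and withdrawals are ignored.

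**Formula.** Mortality among consented children = (M − e)/(1 − e).

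| e, arm 1 vs arm 2 | M = 30% | Ratio | M = 20% | Ratio |
|---|---|---|---|---|
| 5% vs 5% | 26.3% vs 26.3% | 1.00 | 15.8% vs 15.8% | 1.00 |
| 5% vs 6% | 26.3% vs 25.5% | 0.97 | 15.8% vs 14.9% | 0.94 |
| 3% vs 6% | 27.8% vs 25.5% | 0.92 | 17.5% vs 14.9% | 0.85 |
| 5% vs 10% | 26.3% vs 22.2% | 0.84 | 15.8% vs 11.1% | 0.70 |

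Example: (0.30 − 0.05)/0.95 = 0.263, (0.30 − 0.10)/0.90 = 0.222, and 0.222/0.263 = 0.84. Ratios are arm 2 over arm 1. If the larger loss is in the other arm they invert: 0.84 becomes 1.18 and 0.70 becomes 1.42.

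**How many children this takes.** With 216 enrolled per arm, pre-consent deaths number 216 × e/(1 − e). That is 11.4 at 5%, 13.8 at 6% and 24.0 at 10%. The widest scenario is a gap of 12.6 deaths, or 12.6/8 = 1.6 per site over the three-year period.

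**False-positive rate in the widest scenario.** This is a normal approximation with 216 per arm and true equality. At M = 30%, the chance of p < 0.05 is about 17% without clustering and 10% with design effect 2.3. At M = 20% it is about 30% and 16%. The nominal rate is 5%. Using 2.3 assumes that the ICC stated for adherence also holds for mortality.

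**Effect of adding the logged deaths back** (M = 30%, 5% vs 10%). Arm 1: 216 × 0.263 = 56.8 deaths, and (56.8 + 11.4)/(216 + 11.4) = 68.2/227.4 = 30%. Arm 2: 216 × 0.222 = 48 deaths, and (48 + 24)/(216 + 24) = 72/240 = 30%. The ratio returns to 1.00.

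**The case against.** A reader might infer that the plan will produce a false survival difference, or that it favors PEGASUS. The documents support neither. Excluding pre-consent deaths with the arm known is not enough: the share must differ by arm, and nothing in the protocol or SAP shows that it does.

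Several features make a large difference less likely. Randomization was carried out within four groups ranked on baseline enrollment, which is related to how well a site obtains consent. All sites were trained in screening and consent before baseline enrollment. The on-call coordinator is described without any distinction by arm. Site funding follows enrollment in both arms. These points stand. They reduce the risk but do not remove it, and the protocol still names death before consent as a category to be logged.

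The 5% vs 10% scenario is also demanding. At 20% mortality it means that half of all deaths in one arm precede consent. A mild imbalance of 5% vs 6% moves the ratio only to 0.97 or 0.94.

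Protocol 3.7 already states that the study is not sufficiently powered for mortality. That limits how much weight the result can carry, but low power does not protect against bias, and the comparison will still be estimated under a directional hypothesis.

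Finally, exclusion from analysis is inferred from non-enrollment together with consent-based data collection. The SAP population line does not say whether only enrolled children are meant. If another set is intended, the SAP needs to say so.

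**Conclusion.** The point holds in conditional form. As written, the plan yields a mortality ratio among children who survived to consent. That ratio is biased, in either direction, if the share dying before consent differs between arms, and it is unbiased under a true null if the shares are equal. Across the assumed scenarios the ratio runs from 1.00 (equal shares) to 0.84 at 30% mortality or 0.70 at 20%, or the inverse. The assumptions are equal true mortality in both arms, invented values of M and e, and no refusals or withdrawals.

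The documents leave a differential open and do not demonstrate one. The gap is that the log which could reveal it has no place in the SAP. The point concerns a secondary outcome and touches neither the adherence outcome nor the sample size of 432. It is worth correcting because the correction is cheap.

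**What to change.** **SAP Methods item 3:** state that the main in-hospital mortality analysis is conditional on consent, and define the analyzed population.

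**SAP Methods item 4:** prespecify a sensitivity analysis that adds each site's logged pre-consent deaths to both numerator and denominator. Describe its population as consented children plus pre-consent deaths. It should not be called all eligible children, because refused and withdrawn children remain outside it.

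**Reporting:** tabulate eligible, died-before-consent, refused and withdrawn counts by arm and site. Include time from eligibility to consent only if it is already recorded, since section 3.4 mentions reasons for non-enrollment and not times.

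**Cost:** SAP wording, one table and one further model from counts that the log is meant to hold. No change to design, consent procedure or sample size is needed. The added deaths cannot be covariate-adjusted. Ethics approval for aggregate use of unconsented children's deaths must be confirmed first, as the documents do not settle it.
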